Medical Record Documentation: After the medication has been administered, the blinded PI or the physician who completed the injection will document the process in the medical record, specifying how much of the 2mL study drug was used for the injection.

Medication Inventory: Each of the three participating sites will have the same medications for use and they will be stored in locked cabinets and labeled for investigational use only. IDS will provide each site with a drug inventory log to document study drug usage. This drug inventory log will be monitored by the Data and Safety Monitoring Board at intervals specified in this application.

Unfortunately, the use of the local pharmacy (e.g. UUOC pharmacy or FHC pharmacy) will not be a feasible option. This will take at least 30 minutes extra to obtain the medication, for

which will be too time-intensive for most patients to tolerate. Additionally, this will interrupt regular clinic flow to a large degree.

All three medications used in this study have been shown to be safe, and are already used in a standard fashion for intramuscular injections; therefore, these medications will not pose undue risk to the participant. Furthermore, as lidocaine will be included in all injections, the participant will unlikely be able to differentiate which medication they received based off the presence or absence of short-term numbness.

The PI has successfully administered these drugs in the below mentioned dosages and combinations. From past experience, the PI does not express any safety concerns regarding the administration of these drug combinations.

Subsequent injections

Participants will be allowed to have subsequent injections, which is standard practice³⁹⁻⁴³. They may receive up to four injections, spaced at least 1 week apart. The assigned health care professional will access the randomization schema at each subsequent visit to identify which substance was injected at their previous visit and use that same substance for all subsequent injections. The primary time point will be maintained, and questionnaires will be administered.

Medications:

1. 1mL of 1% lidocaine + 1mL of 4mg/mL dexamethasone
2. 1mL of 1% lidocaine + 1mL of 30mg/mL ketorolac
3. 2mL of 1% lidocaine

Outcomes:

1. Pre- and post-injection numeric rating scale (NRS) from 0-10 with regards to the trigger point(s).
2. Survey questions

Primary outcome measure

1. Responder (>50% NRS relief)

Secondary outcome measures

1. NRS improvement

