2. Brief pain inventory (BPI) improvement

Time points:

Participants will fill out a pre-injection survey that contains demographic information and pain- and function-related questions. Participants will also complete a survey at the following time points:

1. Immediately post-injection
2. 1 week post-injection
3. 2 weeks post-injection
4. 4 weeks post-injection
5. 3 months post-injection

Procedures performed for research purposes only:

TPIs are a standard procedure performed by physicians. Regardless of participation in the research study, the procedure will be performed in the same manner.

The research component of this study is to compare the efficacy of three substances used in TPIs with a LTR identified at the time of the injection: a CS (dexamethasone), a NSAID (ketorolac), or only a local anesthetic (lidocaine).

Statistical Methods, Data Analysis and Interpretation

Statistical plan:

Chi-square analysis will be used to identify differences in responders between groups. Repeated-measures ANOVA testing will be used to identify changes in pain scores.

Power Analysis:

Similar to the study by Gerber et al.⁴¹, if 5% of patients spontaneously improve their MTrP status without intervention and aiming for detection of 10% responders, a sample size of 90 subjects would be required. However, in their study, they found that this was substantially overpowered due to a much higher percentage of responders. We have identified a sample size of 60 subjects (20 per group) as being sufficient, based on the prior work being overpowered. As they had a much larger response rate in their actual cohort, we feel that a conservative estimate of 15% responders would be appropriate (as opposed to 10%), which yields a sample size around 60 total subjects.

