**Original Power Analysis:**

Similar to the study by Gerber et al.41, if 5% of patients spontaneously improve their MTrP status without intervention and aiming for detection of 10% responders, a sample size of 90 subjects would be required. However, in their study, they found that this was substantially overpowered due to a much higher percentage of responders. We have identified a sample size of 60 subjects (20 per group) as being sufficient, based on the prior work being overpowered. As they had a much larger response rate in their actual cohort, we feel that a conservative estimate of 15% responders would be appropriate (as opposed to 10%), which yields a sample size around 60 total subjects.

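### Sixty patients (20 per group) do not follow from 5% versus 15% responders, and the plan states no between-arm difference for its three-group chi-square

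*Protocol*

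**What the plan says.** The primary outcome is a binary responder, defined by more than 50% relief on the 0-10 pain scale. Under Statistical plan the protocol says: "Chi-square analysis will be used to identify differences in responders between groups". The Hypothesis section expects ketorolac and dexamethasone to do better than lidocaine alone.

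The Power Analysis borrows from a cited study. It starts from a background rate ("if 5% of patients spontaneously improve their MTrP status without intervention"). Its first sample size is tied to a low responder rate among treated patients: "aiming for detection of 10% responders, a sample size of 90 subjects would be required". It then notes that the cited study saw many more responders than expected, raises the assumed rate, and concludes that "a conservative estimate of 15% responders would be appropriate (as opposed to 10%), which yields a sample size around 60 total subjects". The judgement on group size reads: "We have identified a sample size of 60 subjects (20 per group) as being sufficient, based on the prior work being overpowered".

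No alpha, sidedness, power, dropout allowance or arm-specific rate is given. On treatment, the protocol's study procedures state that "as lidocaine will be included in all injections". The SAP repeats the calculation under Original Power Analysis, down to "which yields a sample size around 60 total subjects".

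**The concern.** Two things look wrong.

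- **The contrast.** A rate in untreated patients is set against one responder rate, but the trial has no untreated arm. The planned test asks whether dexamethasone, ketorolac and lidocaine differ from each other, and the plan never says by how much. A high response rate in earlier work does not fill the gap, because a high rate in every arm says nothing about the difference between arms.
- **The arithmetic.** A ten-point difference between low proportions normally needs well over 100 patients per group, not 20. Calling 15% conservative is also the wrong way round: a larger assumed effect makes the required sample smaller.

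At stake is how the primary result could be read. If nobody knows what difference 20 per arm could detect, a non-significant chi-square cannot be interpreted.

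**Working it through.** **Inputs from the documents:** 5% and 15% (Power Analysis); 60 in total, three equal groups of 20; chi-square between groups. **Assumed, because not stated:** alpha 0.05, 80% power, no dropout.

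**1. Trying to reproduce 60 as a comparison of two groups.** With p1 = 0.05, p2 = 0.15 and mean p = 0.10,

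n per group = [z_α √(2p(1−p)) + z_β √(p1(1−p1) + p2(1−p2))]² / (p2 − p1)²

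Two-sided 0.05: [1.960 × √0.18 + 0.842 × √0.175]² / 0.01 = (0.8315 + 0.3521)² / 0.01 = 140.1.

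| Alpha | n per group, 80% power |
|---|---|
| two-sided 0.05 | 140.1 |
| one-sided 0.05 | 110.2 |
| one-sided 0.10 | 80.2 |

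The arcsine formula, one-sided 0.05, still gives 105 per group. Pooling the two anti-inflammatory arms against lidocaine, one-sided, gives 261 in total. The starting figure of 90 for 5% versus 10% is not reproduced either: the same formula gives 435 per group, two-sided.

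**2. The three-group chi-square (2 df, alpha 0.05), reading 5% and 15% as arm rates.** The noncentrality is n Σ(p_i − p)² / [p(1−p)], with p the mean of the three rates. Exact power enumerates all outcomes at 20 per arm.

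| Rates in the three arms | n per group for 80% (noncentral chi-square) | Exact power at 20 per arm | Asymptotic power at 20 per arm |
|---|---|---|---|
| 5 / 15 / 15% | 149 | 12.0% | 15.9% |
| 5 / 10 / 15% | 174 | 10.9% | 14.3% |
| 5 / 5 / 15% | 111 | 16.7% | 20.1% |

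The sample sizes are approximate: exact power at 149, 174 and 111 per group is 85.7%, 81.9% and 77.4%. A pairwise test of 5% versus 15% with 20 per arm has exact power of 15.4% (Pearson) or 7.0% (Fisher).

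**3. What does come near 60.** A one-sample exact binomial test of all 60 patients against a fixed 5%, rejecting at 7 or more responders, has one-sided size 0.030 and power 81.5% if the true rate is 15%. The same kind of test (one-sided 0.05) with 90 patients and a true rate of 10% has only 55% power, so it does not explain the companion figure. Simple scaling, 90 × 10/15 = 60, matches the stated numbers. That is an inference, and it is not a sample-size formula: under the two-proportion formula the requirement falls about threefold (435 to 141), not 1.5-fold.

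**4. What 20 per arm can detect.** The documents give no lidocaine responder rate, so a range is assumed. Entries are the lowest-to-highest difference, in percentage points, for 80% exact power at alpha 0.05.

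| Lidocaine rate | Three-group, both drugs at the upper rate | Three-group, one drug midway | Unadjusted pairwise Pearson |
|---|---|---|---|
| 30% | 41.1 | 47.2 | 43.9 |
| 40% | 39.7 | 45.5 | 41.8 |
| 50% | 36.8 | 41.9 | 38.6 |
| 60% | 33.0 | 37.2 | 34.5 |

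At the plan's own rates the three-group figures are about 34 (both upper) and 40 (one midway) for 5%, and about 40 and 46 for 15%. At the pairwise extremes in the last column, the three-group test has about 85-86% power (both upper) or 68-73% (one midway).

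**5. Precision.** The Wald 95% half-width is 1.96 √[(p1(1−p1) + p2(1−p2))/20]. If both arms share a rate of 30% to 60% it is about 28 to 31 points, for example 1.96 × √(0.42/20) = 0.284 at 30%. At the detectable differences in step 4 it is about 23 to 28 points.

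**The case against.** The fairest defence is that 5% was meant as a fixed reference, since the plan calls it a rate without intervention. Read that way, 60 pooled patients give about 80% power, so the figure can be computed after all. This stands as far as it goes, and the charge should be worded accordingly: 60 is near the answer to a different question. It does not support a comparison between arms, and it fails for the plan's own 90.

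Alpha and power are unstated, so every required sample size here rests on assumed values. That is true, but the conclusion survives one-sided 0.10.

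The detectable differences use lidocaine rates that the documents do not give. They are labelled as assumed, and the results at 5% and 15% fall inside the same 33 to 47 point range. They are also best case, because they need 20 evaluable patients per arm. With 16 per arm, power in the scenarios with both drugs at the upper rate falls from 80% to about 68-72%. The Wald interval is slightly too narrow at this size. Both points belong in the corrected text.

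Finally, the SAP reports termination after 10 participants, with only two completing all measures, so there is no primary chi-square result to misread. That limits the practical consequence. It does not repair the justification, which the SAP prints again uncorrected.

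**Conclusion.** The concern holds on both counts. The plan gives no between-arm difference for its primary test, and 20 per group does not follow from 5% versus 15% for any conventional between-group calculation. At alpha 0.05 and 80% power (assumed), the pairwise requirement is about 140 per group, seven times the planned 20. The three-group requirement is 111 to 174 per group, roughly five and a half to nine times. Under the plan's own rates read as arm rates, the planned test would have had exact power of 11% to 17%. This is the only justification offered for the size of the trial, so it must be corrected.

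**What to change.** Keep 60. In the protocol and the SAP, remove the 5%/10%/15% derivation and the claim that 20 per group is enough. Because the SAP presents its text as the original plan, a dated correction would keep the record visible. Replace the derivation with a short statement along these lines:

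- The sample size was not derived from a between-arm difference. With 20 evaluable patients per arm, a three-group Pearson chi-square at alpha 0.05 and assumed lidocaine responder rates of 30% to 60%, 80% power needs a difference of about 33 to 41 points if both drugs share the upper rate, and about 37 to 47 points if one drug lies midway.
- If pairwise tests are also cited, give their figure separately (about 35 to 44 points, unadjusted). Name the test and response pattern beside every figure.
- Report responder differences between arms with 95% confidence intervals and name the interval method. The expected Wald half-width is about 28 to 31 points when arms share a rate in that range, and about 23 to 28 points at the detectable differences.
- Do not take a non-significant test as evidence that the drugs do not differ.

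The cost is a few sentences in two documents and a less favourable stated figure. No extra patients are needed.

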**Double-blind, prospective comparison of medications used in trigger point injections –  
ketorolac, lidocaine, or dexamethasone**

**NCT:** 03028012

**PI:** [name]

**Report Date:** April 5, 2017

**Type of Report:** Statistical Plan/Analysis

This study was terminated early due to the lack of enrollment and of participant follow-through to substantiated end of study measures. There was not enough reported data to provide statistically pertinent or relevant analysis based on the original statistical plan and analysis (listed below). The enrollment for this study consisted of 10 participants, 2 males, 8 females. Out of the total number of participants enrolled only two participants completed all study measurement requirements. The remaining eight participants only completed some of the required protocol surveys. Reviewing this study statistically it was decided that there was not enough statistical data to report statistically significant data.

**Original Statistical plan:**

Chi-square analysis will be used to identify differences in responders between groups. Repeated-measures ANOVA testing will be used to identify changes in pain scores.

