Prior studies^{2,3,9,20} demonstrated that most patients obtain significant relief from TPI, but did not identify differences between injection of CS or other substances. However, none of these studies identified LTRs in their injection techniques.

As can be learned from a review of the published literature on muscular trigger points, the cause of this condition is unknown, and no single treatment approach has been established as a clearly accepted gold standard treatment. There is evidence, however, that there is an inflammatory component associated with trigger points and that obtaining a local twitch response is associated with a decrease in local inflammation at the site of a trigger point. The combination of injecting an anti-inflammatory medication and obtaining a local twitch response has never been studied. The purpose of this study is to examine the comparative effectiveness of injectable substances on patient outcome after a TPI with LTR identified, namely a CS (dexamethasone), a NSAID (ketorolac), or only a local anesthetic (lidocaine).

Purpose and Objectives

Hypothesis

The main hypothesis of this study is that anti-inflammatory medications (ketorolac or dexamethasone) will provide longer-lasting and greater pain relief than just lidocaine in trigger point injections where a local twitch response is evoked at the time of the injection.

Purpose/Specific Aims

The primary objective of this study is to compare the efficacy of three substances used in TPIs with a LTR identified at the time of the injection: a CS (dexamethasone), a NSAID (ketorolac), or only a local anesthetic (lidocaine).

Study Population

Age of Participants: 18-100

Sample Size:

At Utah: 60
All Centers: 60

Inclusion Criteria:

1. Men or women age 18 or over
2. At least one active trigger point, as defined by Simons and Travell

Exclusion Criteria:

1. Allergy or contraindication to any NSAID, CS, or local anesthetic
2. Receiving anticoagulant medication
3. History of bleeding disorder
4. Pregnant or breast feeding women
5. Gastrointestinal ulceration
6. Pre-existing renal disease
7. Pre-existing congestive heart failure
8. Diabetes mellitus
9. Prior myocardial infarction or stroke
10. Fibromyalgia

Design

Observational Research

Double Blind

Randomized

Study Procedures

Recruitment/Participant Identification Process:

Subject recruitment

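### The repeated-measures ANOVA of pain scores names no between-arm effect, so the secondary NRS analysis does not say how either anti-inflammatory will be compared with lidocaine

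*SAP*

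**What the plan says.** The protocol (Statistical plan) and the SAP (Original Statistical plan) carry the same two sentences. The first concerns responders: "Chi-square analysis will be used to identify differences in responders between groups". The second concerns pain scores: "Repeated-measures ANOVA testing will be used to identify changes in pain scores". The first states a comparison of arms. The second states no arm term, no interaction, no contrast and no time point.

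The rest of the protocol sets a comparative question. The hypothesis is that "anti-inflammatory medications (ketorolac or dexamethasone) will provide longer-lasting and greater pain relief than just lidocaine", and the objective is to "compare the efficacy of three substances used in TPIs with a LTR identified at the time of the injection". The primary outcome is responder status (more than 50% NRS relief), and "NRS improvement" is listed as a secondary outcome. Under Time points there is a pre-injection survey and five later ones: immediately after injection, then 1 week, 2 weeks, 4 weeks and 3 months. The text on subsequent injections mentions a primary time point but does not say which survey it is.

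**The concern.** A repeated-measures ANOVA in a three-arm trial yields three tests: time, arm, and arm-by-time. Only the last two involve the substances. The sentence does not say which test answers the trial's question, and its literal wording points to time.

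A fall in NRS over time is expected whatever is injected. The background reports that earlier studies found "most patients obtain significant relief from TPI, but did not identify differences between injection of CS or other substances". The protocol also relies on lidocaine being common to every arm ("as lidocaine will be included in all injections"). A significant time effect would therefore be unsurprising if dexamethasone and ketorolac added nothing.

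At stake is the only stated analysis of pain on its 0-10 scale. The size of any additional relief, and how long it lasts, would be estimated there. The responder test reduces NRS to yes or no and cannot give that estimate.

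**Working it through.** **Inputs from the documents.** Three arms, 20 per arm (Power Analysis), so N = 60. There are 1 + 5 = 6 surveys (Time points).

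**Inputs assumed.** The documents give no SD, correlation or expected NRS change. I take SD σ = 2 (range 1.5 to 3), within-patient correlation ρ = 0.5 at all pairs of surveys, α = 0.05, complete data, and a fall of d points after baseline that then persists. The plan gives no power or effect size for the NRS analysis, so it has no figure of its own to reproduce.

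**Step 1: time effect with three identical arms.** The survey means are one value at baseline and five values d lower. Their squared deviations from the overall mean sum to (5d/6)² + 5(d/6)² = 5d²/6. The time sum of squares is then 60 × 5d²/6 = 50d². The error variance is σ²(1 − ρ). The noncentrality is λ = 50d² / [σ²(1 − ρ)], on 5 and (60 − 3) × 5 = 285 degrees of freedom.

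| SD | Fall in every arm | λ | Chance that time is significant |
|---|---|---|---|
| 2 | 1 point | 50/2 = 25 | 98.3% (simulation, 4,000 trials: 98.7%) |
| 2 | 2 points | 200/2 = 100 | 100% (simulation: 100%) |
| 3 | 2 points | 200/4.5 = 44.4 | above 99.9% (simulation: 100%) |
| 3 | 1 point | 50/4.5 = 11.1 | 72% |

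The last row matters: with a small fall and a large SD the time effect is likely but not near-certain. A separate simulation of 3,000 trials with SD 2.5 and a 2-point fall also gave 100%.

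**Step 2: arm tests on the same data.** With identical arms the arm and arm-by-time noncentralities are zero, so each test rejects at its nominal 5%. The simulations gave 4.2% to 5.7%.

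**Step 3: if arm-by-time was intended.** Suppose both anti-inflammatory arms are truly 1 point better than lidocaine at all five later surveys (SD 2). The interaction sum of squares is 20 × (2/3) × (5/6) = 11.1, where 2/3 is the squared spread of the three arms and 5/6 that of the difference over surveys. So λ = 11.1/2 = 5.6 on 10 and 285 degrees of freedom, and power is about 29% (simulation 28%). The arm main effect has about 39% (simulation 40%). The time effect is still significant in 100%. A significant interaction would say only that the three profiles are not parallel. It could come from dexamethasone differing from ketorolac, and it does not give the direction or size of either difference from lidocaine.

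**Step 4: what named contrasts would give.** At one survey, adjusting for pre-injection NRS, the standard error of a two-arm difference is about √[2σ²(1 − ρ²)/20]. With SD 2 this is √(2 × 4 × 0.75/20) = 0.55, so the 95% interval is about ±1.96 × 0.55 = ±1.1 points. With SD 1.5 it is ±0.8, and with SD 3 it is ±1.6. Using change from baseline without adjustment, the standard error is √[2 × 2σ²(1 − ρ)/20] = √(2 × 4/20) = 0.63, so ±1.2 points. The contrast gives a direction, a size and a precision, and baseline adjustment sharpens it.

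**The case against.** The strongest reply is that the sentence is under-specified rather than wrong. It excludes neither an arm factor nor an interaction, and in a randomised trial with a comparative hypothesis a model with arm and time is a natural reading. That stands. A reader might infer that the plan commits to a time-effect test and would present it as evidence of efficacy. The documents do not support that: they name no factor at all, and nowhere do they say that a fall over time would count in favour of a drug.

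It can also be said that the simulation is close to circular, because it builds in a fall and then detects it. That is fair. It shows how uninformative the literal target is, not what the investigators would have done. Its SD, correlation and fall are assumptions.

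The background should not be over-read either. Earlier studies did not identify differences between substances, which is not evidence that none exist. The protocol also sets those studies apart because they did not identify local twitch responses. The expectation of improvement in every arm survives this.

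Finally, the outcome is secondary, the primary test is between groups, and the SAP reports termination with 10 participants, of whom two completed all measurements, leaving too little data to analyse as planned. All of this limits the practical effect.

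The charitable reading does not close the gap. With an interaction included, the plan still names no contrast with lidocaine and no lead survey, so it does not say how the hypothesis would be judged on NRS.

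**Conclusion.** The point holds as a fault in the specification of a secondary analysis. The stated target of the repeated-measures ANOVA does not address the comparative hypothesis. The likeliest alternative, an overall arm-by-time test, does not show which drug is better than lidocaine.

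With 20 complete participants per arm, correlation 0.5 and identical arms, the time effect would be significant in about 98% to 100% of trials for a 1- to 2-point fall at SD 2. It would be significant in about 72% for a 1-point fall at SD 3. The arm and arm-by-time tests stay near 5%. These percentages rest on assumed values. The qualitative conclusion does not, since a time effect common to all arms carries no information on differences between them.

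The primary responder comparison is unaffected. No misleading NRS result has been reported in these documents, so the consequence is for any use of the NRS data and any reuse of the design.

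**What to change.** In both the protocol and the SAP, replace the ANOVA sentence with one that says:

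- The NRS analysis is a repeated-measures model of the post-injection scores with arm, time and arm-by-time, and with pre-injection NRS as a covariate.
- The reported results are the dexamethasone minus lidocaine and ketorolac minus lidocaine differences, each with a 95% confidence interval.
- One follow-up survey, named in advance, leads, and the other surveys are supportive. This also prevents two contrasts at five surveys (2 × 5 = 10 intervals) from carrying equal weight. The survey should be reconciled with the unnamed primary time point in the protocol's text on subsequent injections.
- The overall time effect is descriptive and is not evidence about any substance.

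The cost is wording only: no new data, visits or participants. With the trial stopped, the change serves as a correction for any descriptive use of the data or reuse of the plan.
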